4.2 Efficacy populations

The “All Included Patients” analysis set will be used to show demographic and other baseline characteristics.

The “Per Protocol Patients” analysis set will be used for the primary endpoint analysis of ORR by IRC and for the secondary analyses of ORR by investigator assessment, CR rate and PFS analyses, as well as for OS analyses.

The “All Evaluable Patients” and “All Treated Patients” analysis sets will be used for the secondary endpoint analyses of ORR by IRC, ORR by investigator assessment, CR rate and PFS analyses, as well as for OS analyses.

The “All Responder Patients” dataset will be used for the duration of response (DoR) calculation.

4.3 Safety population

The safety analysis is based on the “All Treated Patients” analysis set.

5 SAMPLE CONSIDERATIONS

The primary endpoint for this study is ORR according to the Lugano classification response criteria per independent review in “Per Protocol Patients” population.

A total of 60 patients with AITL confirmed by central pathological review will be treated, 19 or more responders will be needed to get an overall estimate for response rate higher than 30% and its lower limit for the 95% confidence interval greater than 20% (31.7% CI95% 20.3%–45.0% following the binomial distribution).

The type I error (alpha) associated with this one-sided test is 0.025 and the type II error (beta) is 0.1; hence, statistical power is 90%. The null hypothesis (H0) is set at $ORR \leq 20\%$ ($P_0=0.208$) versus the alternative hypothesis (H1) at $\geq 40\%$ patients ($P_a=0.41$) having an objective response, the variance of the standardized test is under the null hypothesis.

Two futility analyses of the primary endpoint (ORR according to Lugano classification and per IRC) are planned to reject the alternative hypothesis six months after 25% and 50% of eligible patients have been treated (15 and 30 patients, respectively). Pocock boundary and the actual number of patients confirmed by central pathological review will be used to control type II error for both analyses. For example, if there are two or less responders out of 15 patients or seven or less responders out of 30 patients, according to boundaries and sample size assumptions, the alternative hypothesis could be rejected, and thus recruitment might be stopped at the time of the first or second futility analysis, respectively. Otherwise,

accrual will continue to a total of 60 patients AITL confirmed by central pathological review. Active recruitment will not be halted while the analysis is being carried out.

Therefore, if there are 19 or more responders of 60 patients, the null hypothesis can be rejected, allowing consideration of the observed activity plitidepsin as clinically relevant in the setting of patients with AITL.

6 STATISTICAL METHODOLOGY FOR EFFICACY

6.1 *Planned analyses and definitions*

6.1.1 *Primary endpoint analysis*

Objective response is defined as having partial remission (PR) or better as best overall response based on the the Lugano classification response criteria per independent review. The **objective response rate (ORR)** is calculated as the number of objective responders divided by the number of patients in the “Per Protocol Patients” analysis set.

6.1.2 *Secondary endpoints analyses*

The **overall response rate (ORR)** is calculated as the number of objective responders based on the the Lugano classification response criteria per independent review divided by the number of patients in the “All Evaluable Patients” and “All Treated Patients” analysis sets.

The **overall response rate (ORR)** is calculated as the number of objective responders based on the investigator criteria divided by the number of patients in the “Per Protocol Patients”, “All Evaluable Patients” and “All Treated Patients” analysis sets.

The **complete remission rate** is calculated as the number of patients with complete remission based on the the Lugano classification response criteria per independent review or per investigator assessment divided by the number of patients in the “Per Protocol Patients”, “All Evaluable Patients” and “All Treated Patients” analysis sets.

The **duration of response (DoR)** will be analyzed in the “All Responder Patient”. Duration of response will be calculated from the date of first documentation of response to the date of disease progression, recurrence or death with the same censoring rules as PFS. Response will be assessed according to the Lugano classification response criteria per independent central review and investigator assessment.

Progression-free survival (PFS) is defined as the time from the date of first administration to the date of documented progressive disease (PD) or death (regardless of the cause of death). If the patient receives further antitumor therapy (including stem cell transplant) before, PFS will be censored on the date of the last disease assessment prior to the administration of this antitumor therapy. If the patient is lost to follow-up for the assessment of progression the PFS will be censored at the date of last valid tumor assessment. If the patient does not received any drug infusion, he/she will be censored at time zero. Both, independent central review and investigator assessments, will be used for the determination of PFS.

Progression-free survival at 6/12 months (PFS6/PFS12), defined as the Kaplan-Meier estimate of the percentage of patients who are progression-free at six/twelve months after first administration; both independent central review and investigator assessment will be used for the determination of PFS.

Within-patient PFS/TTP, defined as the ratio of the PFS achieved with the experimental treatment versus prior last TTP. Intra-patient PFS/TTP ratio will be categorized and analyzed as a dichotomous variable. Clinical benefit will be defined if a >33% longer PFS/TTP with the experimental treatment vs. the TTP with the immediate prior chemotherapy (ratio >1.33) is achieved.

Overall survival (OS), defined as the time from the date of first administration to the date of death (of any cause) or last patient contact.

Overall survival at 6/12 months (OS6/OS12), defined as the Kaplan-Meier estimate of the percentage of patients who are alive at six/twelve months after first administration.

Treatment safety [AEs, serious adverse events (SAEs) and laboratory abnormalities] graded according to the NCI-CTCAE, v. 4. Dose reductions, skipped doses or dose delays required due to treatment-related AEs, and reasons for treatment discontinuations will be analyzed.

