- (9) Clinical and radiological assessment. When PET-CT is performed it must be in combination with diagnostic quality CT with intravenous contrast (except medically contraindicated). Two alternatives are allowed: Hybrid PET CT scanners may be used to acquire diagnostic quality CT which includes intravenous contrast OR PET CT without intravenous contrast and diagnostic quality CT images with intravenous contrast using a standalone CT scanner must be performed. A PET-CT scan for radiological tumor assessment is required at baseline, one to two weeks after last dose of Cycle 3 and at least four weeks (but no more than 8 weeks) after last dose of Cycle 6 (or earlier in the event of treatment discontinuation for whatever reason; no radiological assessment is necessary in the event of withdrawal due to any reason other than PD during or after Cycle 4 if the Cycle 3 radiological assessment has been performed correctly) or at suspected clinical progression while on treatment. Cycle 4 can be started without waiting for the results of the Cycle 3 tumor assessment. The End of Cycle 6 visit should take place 4–8 weeks after last dose of Cycle 6 (when the PET-CT results are available). If a patient is shown to have SD or PR at this assessment, treatment can resume (Cycle 7), and tumor assessment may be evaluated by CT scans every four months (+ 2 weeks) for the first two years and every six months (+ 2 weeks) thereafter, but any subsequent improvement in response should be confirmed by PET-CT. If a patient is shown to have CR or PD, the patient should be discontinued and the EOT visit performed as soon as possible. Disease progression at any time during the study should be confirmed by imaging (if the physical condition of the patient permits).
- (10) Clinical and radiological assessment. A CT scan may be used for radiological tumor assessment of patients who showed clinical benefit (SD, PR, CR) every four months (+2 weeks) for the first two years of follow-up, and every six months (+2 weeks) thereafter, unless clinically indicated. In the case a patient continues in treatment beyond Cycle 6 (see section [5.2.1.2](#)), CT may be used but any subsequent improvement in response should be confirmed by PET-CT.

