APL-B-013-02 (53, 54)	A Phase II multicenter, open-label, clinical and PK study of plitidepsin as a 1-hour weekly iv infusion, in patients with relapsed or refractory aggressive non-Hodgkin lymphoma	Plitidepsin 3.2 mg/m  (1-h i.v.)	64	Non-cutaneous PTCL (n=29): 2 CR and 4 PR as per the IWG criteria for NHL (ORR: 20.7%). Median TTP/PFS = 1.6 months; median OS = 10.2 months. AITL (subgroup included in PTCL cohort; n=9): 2 CR and 1 PR as per the IWG criteria for NHL (ORR: 33.3%). Duration of response of 121, 12 and 4 weeks. Other lymphomas (n=30): No objective responses as per the IWG criteria for NHL. Median TTP/PFS = 1.3 months; median OS = 4.5 months.

Study	Study design and objectives	Dose (infusion)	Treated patients	Efficacy (objective response or TTP > 3 months)
APL-B-015-04 (55)	A Phase II multicenter, open-label, clinical and PK study of plitidepsin as a 1-hour weekly iv infusion, in patients with relapsed or refractory acute lymphoblastic leukemia	Plitidepsin 3.2 mg/m  (1-h i.v.)	17	( n=13 ): No complete or partial remissions. Median PFS = 0.6 months, median OS = 2.1 months.

\*All 19 patients were first given plitidepsin alone in this study, and after showing suboptimal response their treatment was supplemented with dexamethasone.

The underlined n value shown in the efficacy column refers to patients evaluable for efficacy.

CLL, chronic lymphocytic leukemia; CR, complete remission/complete response; i.v., intravenous; IWG, International Working Group; IWG-MRT, International Working Group for Myelofibrosis Research and Treatment; MR, minimal response; NCI, National Cancer Institute; NHL, non-Hodgkin lymphoma; ORR, overall response rate; OS, overall survival; PFS, progression-free survival; PK, pharmacokinetic; p.o., orally; PR, partial remission/partial response; PTCL, peripheral T-cell lymphoma; q4wk, every four weeks; SD, stable disease; TTP, time to progression.

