4.1 Analysis sets definitions

“All Included Patients” analysis set is defined as all patients who are included in the study (excluding patients who signed informed consent but are classified as screening failures), independent of whether they received the study drug.

“All Treated Patients” analysis set is defined as all included patients who receive at least part of one dose or infusion of plitidepsin.

“Per Protocol Patients” analysis set is defined as all eligible and treated patients with AITL diagnosis confirmed after central pathological review.

“All Evaluable Patients” analysis set is define as all eligible patients with AITL diagnosis confirmed after central pathological review who receive at least two plitidepsin cycles in which at least two complete infusions have been administered and had at least one disease assessment as well as in patients who discontinue treatment without Cycle 3 tumor assessment after at least two plitidepsin infusions due to disease progression (PD) (or death due to PD) or toxicity (or death due to toxicity), defined as “early PD” and “treatment failures” respectively.

“All Responder Patients” analysis set is defined as all patients with CR or PR as overall best response.

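### SAP 6.1.2 has no PFS rule for a treated patient with clinical progression, no post-baseline scan and a switch of therapy; that patient can be censored before first dose, which biases PFS upward.

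*SAP*

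**What the plan says.** SAP 6.1.2 runs PFS from first administration to "the date of documented progressive disease (PD) or death (regardless of the cause of death"). The next rule is conditional. If further antitumor therapy, stem cell transplant included, is given before that event, "PFS will be censored on the date of the last disease assessment prior to the administration of this antitumor therapy". For a patient lost to follow-up for progression, "the PFS will be censored at the date of last valid tumor assessment". The only time-zero rule is for the undosed: "If the patient does not received any drug infusion, he/she will be censored at time zero".

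Three other places bear on who reaches these rules.

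- SAP 4.1 foresees patients who "discontinue treatment without Cycle 3 tumor assessment after at least two plitidepsin infusions due to disease progression (PD) (or death due to PD") and labels them early PD.
- Footnote 9 of the protocol's Schedule of Assessments requires PET-CT at suspected clinical progression on treatment, and earlier than scheduled if treatment stops. The waiver covers only non-PD withdrawals during or after Cycle 4 with a correct Cycle 3 scan. The same footnote says: "Disease progression at any time during the study should be confirmed by imaging (if the physical condition of the patient permits").
- Protocol 5.4 (Table 4) places the baseline scan within 28 days before Day 0, hence before first dose.

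The IRC assigns progression and censoring dates under an algorithm kept in a separate charter (Protocol 3.1). Time-to-event endpoints are exploratory (Protocol 9.2.1, SAP 6.2.2).

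**The concern.** The event definition depends on the word documented, which neither document defines, while the protocol accepts that some progression will not be imaged. Suppose a dosed patient deteriorates, is judged by the investigator to have progressed, is not scanned, and starts another therapy while alive. If clinical progression is not documented progression, the new-therapy rule applies. If disease assessment means the scan, the last one is at baseline. The censoring time is then zero or negative, and the patient never enters the risk set.

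That censoring is informative, because it removes patients for the reason PFS is meant to measure. The missing fallback also reaches patients who stop for toxicity, or are lost, before any post-baseline assessment.

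At stake are PFS, PFS6 and PFS12, which fill six tables (SAP Tables 11.3.2.22 to 11.3.2.27) and feed the Cox models. DoR uses the same censoring rules, but a responder has by definition had a post-baseline assessment, so this gap does not touch it. The SAP plans no alternative censoring analysis for PFS, so the bias would go unmeasured.

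**Working it through.** The documents give no planned or expected PFS figure for this trial, so there is nothing of the plan's own to reproduce.

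**1. Which patients the rules reach**

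| Treated patient | Treatment under SAP 6.1.2 |
|---|---|
| Dies before any new therapy, scanned or not | Event |
| PD documented, including on an unscheduled scan | Event |
| Early PD by SAP 4.1, with a scan at suspected progression or at stopping | Event if that scan documents PD |
| Clinical PD, no post-baseline scan, new therapy first, alive | Not settled; can be censored at the baseline scan |
| Toxicity stop or loss to follow-up before any post-baseline assessment | Censored; no usable date given |

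Only the fourth row produces the upward bias described here.

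**2. Timing of the first scheduled scan**

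With no delays, Cycle 3 Day 15 is study Day 28 + 28 + 15 = 71. The scan is due 7 to 14 days later, on Day 78 to 85, which is 77 to 84 days after first dose: 77/30.4375 = 2.53 months to 84/30.4375 = 2.76 months.

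Protocol Table 1 reports, for the earlier non-cutaneous PTCL cohort (n=29), "Median TTP/PFS = 1.6 months; median OS = 10.2 months". Assuming exponential PFS, the share failing before time t is 1 − 0.5^(t/median):

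- median 1.6 months: 1 − 0.5^(2.53/1.6) = 67%, and 1 − 0.5^(2.76/1.6) = 70%
- median 3.0 months (assumed): 44% to 47%

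These are shares failing before the *scheduled* scan. They show that early failure may be common. They are not estimates of how many patients would lack a scan.

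**3. Effect on PFS6**

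Let c be the number of the 60 patients in the fourth row, and S the number progression-free at 6 months, with no other censoring. Counted as events, the c patients give PFS6 = S/60. Censored at or before time zero, they leave the risk set and PFS6 = S/(60 − c). The ratio of the two is 60/(60 − c).

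| c (assumed) | S = 12 | S = 15 | S = 18 |
|---|---|---|---|
| 0 | 20.0% | 25.0% | 30.0% |
| 3 | 21.1% | 26.3% | 31.6% |
| 6 | 22.2% | 27.8% | 33.3% |
| 9 | 23.5% | 29.4% | 35.3% |
| 12 | 25.0% | 31.2% | 37.5% |

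For example, 15/57 = 26.3% and 15/48 = 31.2%. The relative inflation is 60/57 = 1.05 for c = 3 and 60/48 = 1.25 for c = 12. PFS12 is inflated by the same ratio under the same assumption. Neither c nor S comes from the documents.

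**The case against.** A reader might infer that all early-PD patients are censored at baseline and vanish from the curve. The documents do not support that. The censoring sentence applies only when new therapy precedes documented PD or death, and lacking the Cycle 3 assessment is not the same as lacking any post-baseline scan. Nor does a first scheduled scan at 2.5 to 2.8 months imply that two thirds of patients go unassessed, because suspected progression or early stopping itself requires a scan.

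Four further arguments have weight.

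- The new-therapy rule refers to a disease assessment, and the protocol describes assessments as clinical and radiological. A later clinical assessment could set the date. Baseline-scan censoring is therefore one reading, which is why the text needs settling.
- The IRC charter is not among the documents and may resolve the IRC dates. It would not settle investigator PFS.
- SAP 8.3 already plans time to first subsequent therapy or death, and Table 11.3.2.28 shows IRC-investigator concordance on events and censoring. The first does not count progression as an event. The second shows disagreement but does not isolate these patients or correct the curve.
- Entering an investigator's stopping reason into the main IRC analysis would weaken its independence. This stands, and the fix respects it.

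On the other side, a missed scan is unlikely to be recovered later. The end-of-treatment list (Protocol 5.10) contains no tumor assessment, and follow-up imaging is required only for patients who showed clinical benefit (5.11).

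**Conclusion.** The gap is real but narrow. It affects dosed patients with clinical progression, no post-baseline imaging, and new therapy begun before documented progression or death. For them the plan permits a censoring date before first dose, and the resulting bias in PFS, PFS6 and PFS12 is upward. At an assumed PFS6 of 25.0%, it is about 1 percentage point with 3 such patients in 60 and about 6 points with 12. It is nil if the required scans are done. These sizes rest on an assumed count, no other censoring, and the reading that clinical progression is not documented progression and that the last assessment is the baseline scan. For IRC PFS they also depend on a charter not available here.

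No decision rule uses PFS, and the primary ORR keeps every Per Protocol patient in its denominator. The point does not threaten the trial's conclusion, but should be settled before PFS is analyzed.

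**What to change.** In SAP 6.1.2:

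1. **Investigator PFS.** Count investigator-determined progression without evaluable imaging as an event, on the date the investigator recorded the progression. Do not use the end-of-treatment date, which by convention falls 30 days after the last dose. Do not tie the rule to the early-PD class in 4.1, which requires at least two infusions.
2. **IRC PFS.** Keep the charter algorithm. Censor treated patients with no post-baseline assessment at Day 1, and report their number and reasons (clinical PD, toxicity, lost to follow-up). This leaves any bias in the main IRC estimate but makes the affected patients visible.
3. **Sensitivity analysis.** Pre-specify one, for both IRC and investigator PFS, in which discontinuation for clinical PD without imaging, or the start of any new antitumor therapy other than SCT in documented PR or CR, is an event.

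The cost is a few sentences, one extra set of PFS output, and possibly a somewhat shorter reported PFS. The data needed are already collected.

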### **5.2.1.2 Reasons for Treatment Discontinuation**

Patients will receive study treatment until:

- Disease progression (PD).
- Maximum of six cycles unless the patient is in:
  - PR 4–8 weeks after last dose of Cycle 6: in accordance with Investigator decision, the patient may then continue in treatment until CR or progression.
  - SD 4–8 weeks after last dose Cycle 6: in accordance with Investigator decision, the patient may then continue until CR or progression.
- If patient is in CR after six treatment cycles, treatment should be stopped.
- The patient achieves PR or CR at any time during the planned six cycles and is eligible for consolidation with autologous or allogeneic stem cell transplant (SCT) as per Investigator criteria.
- There is unacceptable toxicity.
- There is intercurrent illness of sufficient magnitude to preclude safety continuation of the study.
- There is patient refusal and/or non-compliance with study requirements.
- Investigator's decision.
- There is a protocol deviation with an effect on the risk/benefit ratio management of the patient.
- There is a treatment delay > 15 days from the treatment due date (except in case of clear clinical benefit and with the Sponsor's approval).
- There is a requirement of > 2 dose reductions (except in case of clear clinical benefit and with the Sponsor's approval).

Patients who are withdrawn for any reasons must not be re-treated in the context of this study at any time. For follow-up activities, please refer to Section [5.11](#).

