Table 11.3.2.21 Time to response (Investigator assessment and “All Responder Patients” population)

N	X
Median	X
Minimum	X
Maximum	X.X

Table 11.3.2.22 PFS (Independent Review assessment and “Per Protocol Patients” population)

N	X
Events	X
Censored	X
Median PFS	X.X
PFS at 6 months	X.X
PFS at 12 months	X.X

Kaplan-Meier plot will be also shown (Figure 11.3.2.22)

Table 11.3.2.23 PFS (Independent Review assessment and “All Evaluable Patients” population)

N	X
Events	X
Censored	X
Median PFS	X.X
PFS at 6 months	X.X
PFS at 12 months	X.X

Kaplan-Meier plot will be also shown (Figure 11.3.2.23)

Table 11.3.2.24 PFS (Independent Review assessment and “All Treated Patients” population)

N	X
Events	X
Censored	X
Median PFS	X.X
PFS at 6 months	X.X
PFS at 12 months	X.X

Kaplan-Meier plot will be also shown (Figure 11.3.2.24)

Table 11.3.2.25 PFS (Investigator assessment and “Per Protocol Patients” population)

N	X
Events	X
Censored	X
Median PFS	X.X
PFS at 6 months	X.X
PFS at 12 months	X.X

Kaplan-Meier plot will be also shown (Figure 11.3.2.25)

Table 11.3.2.26 PFS (Investigator assessment and “All Evaluable Patients” population)

N	X
Events	X
Censored	X
Median PFS	X.X
PFS at 6 months	X.X
PFS at 12 months	X.X

Kaplan-Meier plot will be also shown (Figure 11.3.2.26)

Table 11.3.2.27 PFS (Investigator assessment and “All Treated Patients” population)

N	X
Events	X
Censored	X
Median PFS	X.X
PFS at 6 months	X.X
PFS at 12 months	X.X

Kaplan-Meier plot will be also shown (Figure 11.3.2.27)

Table 11.3.2.28 PFS – Concordance between Independent Review assessment and Investigator assessment (“Per Protocol Patients” population)

	N	%
Event by investigator		
Agreement on event		
Same date		
Later date		
Earlier date		
Censored by investigator		
Agreement on censoring		
Same date		
Different date		
Agreement on status		
Agreement on status and date		

Table 11.3.2.29 Intra-patient PFS/TTP ratio (Independent Review assessment and “Per Protocol Patients” population)

Ratio		
	N	%
≤1.33	X	X.X
>1.33		

Table 11.3.2.30 Intra-patient PFS/TTP ratio (Independent Review assessment and “All Evaluable Patients” population)

Ratio		
	N	%
≤1.33	X	X.X
>1.33		

Table 11.3.2.31 Intra-patient PFS/TTP ratio (Independent Review assessment and “All Treated Patients” population)

Ratio		
	N	%
≤1.33	X	X.X
>1.33		

Table 11.3.2.32 Intra-patient PFS/TTP ratio estimates (Independent Review assessment and “Per Protocol Patients” population)

	Proportion	Lower 95% limit	Upper 95% limit
Ratio	X.X	X.X	X.X

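### The PFS/TTP ratio is split at 1.33 with an exact binomial CI as if every patient's status were known, although PFS can be censored before the ratio is decided

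*SAP*

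**What the plan says.** SAP 6.1.2 defines the endpoint: "Within-patient PFS/TTP, defined as the ratio of the PFS achieved with the experimental treatment versus prior last TTP". It then states that "Intra-patient PFS/TTP ratio will be categorized and analyzed as a dichotomous variable", and that clinical benefit requires PFS more than 33% longer than the "TTP with the immediate prior chemotherapy (ratio >1.33) is achieved".

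The same section sets the censoring rules for PFS. For new therapy, including stem cell transplant, "PFS will be censored on the date of the last disease assessment prior to the administration of this antitumor therapy". For loss to follow-up, "the PFS will be censored at the date of last valid tumor assessment". SAP 3.3 lets PFS run to progression, death or the last tumor evaluation, so a censored patient still has a numeric PFS.

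In SAP Appendix I, 11.3.2, the shells that begin with "Table 11.3.2.29 Intra-patient PFS/TTP ratio" (11.3.2.29-31 for independent review, 11.3.2.35-37 for the investigator) have only the rows ≤1.33 and >1.33. Tables 11.3.2.32-34 and 38-40 give the proportion with an exact binomial 95% CI. The response tables in the same appendix do carry a not-evaluable row.

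Protocol 9.2.1 and SAP 6.2.2 plan Kaplan-Meier for DoR, PFS and OS, not for the ratio. Protocol 5.2.1.2 lists among the reasons to stop treatment: "The patient achieves PR or CR at any time during the planned six cycles and is eligible for consolidation with autologous" or allogeneic transplant.

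**The concern.** A binomial proportion needs a known yes or no for every patient. When PFS is censored, only a lower bound on the ratio is known. If that bound is still at or below 1.33, the patient's status is open, but a two-row table has nowhere to put an open status. Take a responder censored at 4 months with a prior TTP of 5 months. The observed ratio is 4/5 = 0.80, so the patient lands in ≤1.33, yet would count as a benefit if progression came after 1.33 × 5 = 6.65 months.

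The patients at issue are progression-free when censored, and some leave in remission for transplant. Counting them as no benefit can only lower the reported rate. At stake is a named secondary endpoint that the SAP uses to define clinical benefit and that fills twelve tables. The choice of rule should also not be left until the data are seen.

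**Working it through.** **1. The plan's own exact interval.** No figure is stated for the ratio. The same method is applied to ORR in SAP 5. Clopper-Pearson for 19/60 gives 31.67% (20.26-44.96), which matches the stated 31.7% (20.3-45.0). The formula is sound.

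**2. Who is unresolved.** Let C be the censored PFS and T the prior TTP. True PFS is at least C, so the true ratio is at least C/T.
- If C/T > 1.33, the true ratio exceeds 1.33 and the patient is correctly a benefit.
- If C/T ≤ 1.33, equivalently T ≥ C/1.33, the status is unknown.

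**3. When this happens on the protocol schedule** (28-day cycles, no delays, 30.44 days per month):
- Cycle 3 scan: the last dose of Cycle 3 is 2 × 28 + 14 = 70 days after first dose. Adding 1-2 weeks gives 77-84 days, or 2.53-2.76 months. A responder censored there is unresolved if prior TTP was at least 2.53/1.33 = 1.9 to 2.76/1.33 = 2.1 months.
- End of Cycle 6 scan: the last dose is 5 × 28 + 14 = 154 days after first dose. Adding 4-8 weeks gives 182-210 days, or 5.98-6.90 months. The threshold is 5.98/1.33 = 4.5 to 6.90/1.33 = 5.2 months.

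**4. Effect on the reported rate.** Assume n = 60, x = 15 patients observed above 1.33, and c unresolved. The counts are assumptions, because the documents give no censoring rate.

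| c | Counted as ≤1.33: x/n | Dropped: x/(n−c) | Counted as >1.33: (x+c)/n |
|---|---|---|---|
| 3 | 25.0% (14.7-37.9) | 26.3% (15.5-39.7) | 30.0% (18.8-43.2) |
| 6 | 25.0% (14.7-37.9) | 27.8% (16.5-41.6) | 35.0% (23.1-48.4) |
| 9 | 25.0% (14.7-37.9) | 29.4% (17.5-43.8) | 40.0% (27.6-53.5) |

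The undetermined width is c/n: 3/60 = 5 points, 6/60 = 10, 9/60 = 15.

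**5. Bias by simulation, two sets of assumptions.**
- *Correlated exponential times*: n = 60, median prior TTP 3-6 months, median PFS 2-4 months, correlation 0-0.4, 10-20% of patients transplanted progression-free at 3.5-6.5 months. Between 3% and 13% of patients are misfiled and the reported rate is 1-5 points low. One case near the top of that range reports 35.3% against a true 39.9%. Kaplan-Meier on the ratio is 1-4 points high.
- *Log-normal times*: both medians 4 months, true P(ratio > 1.33) about 40%, about one third of patients responding, transplanted responders censored at 3 months:

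| Responders transplanted | Mean unresolved of 60 | Counted as ≤1.33 (CI coverage) | Dropped | Counted as >1.33 | Kaplan-Meier on ratio |
|---|---|---|---|---|---|
| 0% | 0 | 40% (96%) | 40% | 40% | 40% |
| 25% | 3.9 | 36% (92%) | 39% | 43% | 40% |
| 50% | 7.9 | 32% (76%) | 37% | 45% | 39% |
| 75% | 11.9 | 28% (51%) | 35% | 48% | 39% |

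Without censoring the planned method behaves as it should. With censoring the face-value estimate falls, and dropping the unresolved patients removes only part of the bias. The two bounds bracket the true value in every row. The last two rows assume heavy transplant use (on average 9.6 and 14.4 of 60 patients) and are stress cases.

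**The case against.** The strongest reply is that the plan is silent rather than wrong. No sentence in either document says that a censored patient counts as no benefit. Table shells are layouts, and SAP 8.8, which leaves missing values out of the calculations, might be read as dropping an undecided ratio. This stands as a limit on the claim: the misfiling follows from applying the shells to PFS as SAP 3.3 defines it. It does not remove the problem, because dropping these patients also ignores the censoring and gives a different, still biased, number.

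Three stronger readings are tempting and are not supported:
- *All patients censored progression-free, or the best responders generally, are misclassified.* Only those censored at or below 1.33 are affected.
- *The exact CI is itself wrong.* The method is valid for a known binary outcome. The fault is applying it where some outcomes are unknown.
- *Responders are expected to leave for transplant.* Protocol 5.2.1.2 makes it one of several reasons to stop, at the investigator's judgement, and no rate is given. The rate could be low: Protocol 1.1.1 describes a mostly elderly population, and SAP 1 notes that both earlier AITL complete responders had already failed transplant-supported therapy. The assumed 10-20% means 6-12 of 60 patients, or 32-63% of 19 responders.

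It is also fair that the likely bias is small beside sampling error (the exact CI at 35% of 60 is about 25 points wide), that it runs against the drug, and that the PFS tables show censored counts. None of this tells a reader of the ratio tables how many statuses are unknown.

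**Conclusion.** The concern holds in this limited form. Applied as written, the two-row shells and exact CI treat every patient's ratio as decided. Patients censored progression-free at or below 1.33 then count as no benefit, and the rate is biased down. Under assumed rates the bias is about 1-5 points, and more only if transplant in remission is common. Three to nine unresolved patients of 60 leave 5-15 points undetermined. Both figures rest on censoring, TTP and PFS assumptions that the documents neither give nor contradict.

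A reader might infer that the trial's conclusion is at risk. It is not: the ratio has no hypothesis or decision rule, SAP 6.2.2 treats time-to-event endpoints as exploratory, and the primary ORR analysis does not use the ratio. A reader might also infer that Kaplan-Meier should replace the binomial estimate. The working does not support that: it was 1-4 points high in one simulation and within about 1 point in the other, and censoring at transplant in remission is probably informative.

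**What to change.** - In Tables 11.3.2.29-31 and 35-37, add a row: *undetermined: PFS censored, ratio ≤1.33*.
- In Tables 11.3.2.32-34 and 38-40, report the proportion above 1.33 with its exact CI twice, counting undetermined patients first as ≤1.33 and then as >1.33.
- Beside these bounds, add the Kaplan-Meier estimate of P(ratio > 1.33) with its CI as a supportive analysis, and note that it assumes non-informative censoring.
- State the rule in SAP 6.1.2, including that a patient censored above 1.33 counts as >1.33.

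The cost is SAP wording and a few lines of programming. The downside is that a range is reported in place of one number. Sample size, data collection and the ORR analysis do not change.
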